The SGB was first proposed to treat olfactory dysfunction by Lee et al in 2003, where 38 post-viral olfactory dysfunction participants were treated with SGB and 13 participants remained untreated as controls.²² Subjective olfactory function improved in 27 (71%) of the treated participants compared to zero (0%) of the controls. Olfactory perception was improved significantly in the SGB group assessed both by the butanol threshold test and odor identification test. There were no complications of SGB in the 38 treated participants. Another study in 2007 by Moon et al found that in 13 participants with various etiologies of olfactory dysfunction, seven (54%) demonstrated improvement with repeated SGBs.²³ The same group conducted a study published in 2013 looking at the long-term results of SGB in treating olfactory dysfunction from various etiologies. Of 37 participants with olfactory dysfunction unresponsive to oral or intranasal steroids who underwent SGB, 15 (41%) were determined to be responsive and 22 (59%) unresponsive to the treatment. Importantly, the responsive group had a mean duration of olfactory dysfunction of 1.6 years vs. a mean duration of olfactory dysfunction of 4 years in the unresponsive group. The study found that in those who respond to SGB, the beneficial effects on olfaction last at least 5 years. Of the 37 treated participants there was only 1 who experienced a complication, which was a temporary brachial plexus block.

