Clinical Global Impression - Improvement Scale (CGI-I). The overall response to treatment will be measured with the *CGI-I* scale. The *CGI-I* Scale measures response to treatment for a number of disorders and has good internal consistency and validity. {Dunlop, 2017, Transdiagnostic Clinical Global Impression Scoring for Routine Clinical Settings} The *CGI-I* scale measures change in clinical condition based on a 7-point Likert scale and will be modified as seen in the Appendix. The primary outcome measure of the study will be the proportion of participants within each *CGI-I* for smell loss group at 1 month. Responders will be identified as those reporting moderate improvement or greater.

Long-COVID Questionnaire. We will assess the following 11 symptoms of Long COVID other than olfactory and gustatory dysfunction: tiredness/fatigue, shortness of breath, brain fogginess, headache, cough, depression, low-grade fevers, palpitations, dizziness,

muscle pain, and joint pains. All 11 symptoms will be asked to rank the level of severity with answer choices from *No problem* to *Severe problem*. The Long-COVID questionnaire will be administered at all 3 visits. See Appendix for questionnaires.

Patient Satisfaction with Treatment. Patients will be asked at the final visit, “Overall, how satisfied were you with the stellate ganglion block treatment for your smell loss?” Possible answer choices: 1) Completely dissatisfied, 2) Mostly dissatisfied, 3) Somewhat dissatisfied, 4) Neither satisfied or dissatisfied, 5) Somewhat satisfied, 6) Mostly satisfied, 7) Completely satisfied. Patients will also be asked at the final visit, “Would you recommend this treatment to a family member or close friend who also suffers from chronic smell loss due to COVID-19?” Possible answer choices: 1) Yes, 2) No.

Adverse Events. Participants will be asked to describe any adverse events experienced after both SGB procedures. Additionally, any adverse events noted at the time of SBG will be noted.

D Investigational Agent

D1 Clinical Data to Date

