Inclusion/Exclusion Criteria	X		
UPSIT	X	X	X
ODOR Questionnaire	X	X	X
Long-COVID Questionnaire I	X		
Long-COVID Questionnaire II		X	X
Smell and Taste Questionnaire I	X		
SGB	X	X	
Smell and Taste Questionnaire II		X	X
Participant Satisfaction with Treatment Questionnaire		X	X
Adverse Events	X	X	X

F3 Safety and Adverse Events

3.a Safety and Compliance Monitoring

The specific monitoring plan for this study is based on the potential risk of participation and size and complexity of the planned investigation. Based on these considerations, this study will have a monitoring board comprised of [name], [name], [name], [name], and [name], the study biostatistician. The monitoring board will meet to review data after enrollment of 10 participants. All reports of a Serious Adverse Event (SAE) or an Unexpected Adverse Event will be investigated by the monitoring team and reported to Washington University HRPO according to the reporting requirements.

3.b Adverse Events

Adverse events will be tracked from the time of dose administration through post dose and at the follow up visit 3 for drug-related adverse events. All adverse events will be documented and assessed for relatedness to the study medication. The study team will monitor for adverse events on an ongoing basis. Once the team becomes aware of an adverse event, the AE will be reported according to institutional guidelines.

G Statistical Plan

G1 Sample Size Determination and Power

Sample size estimate for the proposed study is based both on feasibility and previous data on the use of SGB for non-COVID-19 post-viral olfactory dysfunction.

A power analysis was performed using Fisher's exact test in G-Power 3.1.2. With a positive response based on the previous study expected in 71% of participants,²² we estimate that a total sample size of 20 participants will result in a 95% confidence interval of 0.71 (+/- 0.21), resulting in a true response rate likely between 50% and 92%. A total of 20 participants are needed to allow us to detect with 80% power at the 2-sided alpha level of 0.05 a within-subjects response rate of 50% or more in the percent of subjects who experience a clinically meaningful change in CGI-I score.

G2 Analysis Plan

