Standard descriptive statistics will be used to describe distribution of baseline characteristics in each of the study groups. The effect of the intervention will be measured as the proportion of participants reporting that their sense of smell is moderately better or much better than before undergoing a stellate ganglion block. Intention to treat principles will be followed.

The 95% confidence interval around this effect size will be determined to assess the precision of the observed effect and whether a clinically meaningful difference is plausible given the observed results. Appropriate analyses will be performed for the secondary outcome measures.

H Data Handling and Record Keeping

H1 Confidentiality and Security

The secure REDCap database will be used to store data. Only study team members will have access to the database.

I Study Monitoring, Auditing, and Inspecting

I1 Study Monitoring Plan

The specific monitoring plan for this study is based on the potential risk of participation and size and complexity of the planned investigation. Based on these considerations, this study will have a monitoring board comprised of [name], [name], [name], [name], and [name], the study biostatistician. The monitoring board will meet to review data after enrollment of 10 participants. All reports of a Serious Adverse Event (SAE) or an Unexpected Adverse Event will be investigated by the monitoring team and reported to Washington University HRPO according to the reporting requirements.

J Attachments

J1 Questionnaires or surveys

- ODOR questionnaire
- Symptom Burden Questionnaire
- Long COVID
- Smell and Taste Questionnaire I
- Smell and Taste Questionnaire II

K References

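### The 50% to 92% interval in G1 has about the right width but sits 3 to 4 points too high; at 14/20 the exact 95% interval is 46% to 88%

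*Combined protocol and SAP*

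**What the plan says.** Section G1 bases the sample size on feasibility and on earlier data. It takes its planning rate from one study: "With a positive response based on the previous study expected in 71% of participants". It then states the expected precision with 20 participants: a "95% confidence interval of 0.71 (+/- 0.21), resulting in a true response rate likely between 50% and 92" percent. No interval method is named. A separate sentence gives the power statement: "detect with 80% power at the 2-sided alpha level of 0.05 a within-subjects response rate of 50% or more".

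Section B (repeated in D1) describes the source of the 71%: "Subjective olfactory function improved in 27 (71%) of the treated participants", 27 of 38 people with post-viral loss. It gives no threshold for improvement. The same section reports 7 of 13 (54%) and, from a third study, "15 (41%) were determined to be responsive" (15 of 37). Both of those cohorts had various etiologies.

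Section C3 sets this trial's responder rule: "Responders will be identified as those reporting moderate improvement or greater". For the analysis, G2 says "The 95% confidence interval around this effect size will be determined", again with no method named.

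**The concern.** The usual normal-approximation interval for 0.71 at n=20 has a half-width of 0.199, not 0.21, so the stated figure needs explaining. A symmetric interval is also a poor description of a proportion near 0.7 with 20 people, because the binomial distribution is skewed there and the correct limits are pulled towards 50%.

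Two things are at stake. First, a reader of G1 takes 50% as the floor for the expected result, and a properly placed interval goes lower. Second, the interval for the responder proportion is the only inference that G2 spells out. If G1's form is reused there, the published limits for a result near 70% will be too high. The planning rate adds a smaller question: the protocol does not show that the earlier study's improvement corresponds to this trial's moderate-or-greater rule.

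**Working it through.** **Inputs.** p = 0.71 and n = 20 (G1); 95% two-sided (G1, G2); other cited rates 54% and 41% (section B).

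**1. Reproduce the plan's figure.** The standard error is sqrt(0.71 × 0.29 / 20) = 0.1015.

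| Method at n=20, p=0.71 | Half-width | Limits |
|---|---|---|
| Symmetric, z = 1.96 | 0.199 | 51.1% to 90.9% |
| Symmetric, t(19) = 2.093 | 0.212 | 49.8% to 92.2% |
| Symmetric, z with n−1 in the standard error | 0.204 | 50.6% to 91.4% |
| Symmetric, z with continuity correction | 0.224 | 48.6% to 93.4% |
| Exact, interpolated at x = 14.2 | 0.210 | 46.7% to 88.8% |

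Of these, only the t(19) version gives both stated limits after rounding. The exact interval shares the half-width but lies lower.

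**2. Intervals at the nearest attainable count.** No result out of 20 equals 71%; the nearest is 14/20 = 70%.

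- Exact (Clopper-Pearson): lower = Beta quantile (0.025; 14, 7) = 45.7%; upper = Beta quantile (0.975; 15, 6) = 88.1%. Width 42.4 points.
- Wilson: centre (0.70 + 0.0960)/1.1921 = 0.668; half-width 1.96 × sqrt(0.0105 + 0.0024)/1.1921 = 0.187; limits 48.1% to 85.5%.
- Symmetric with t(19): 0.70 ± 2.093 × 0.1025 = 48.6% to 91.4%.
- Symmetric with z: 49.9% to 90.1%.

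All four lower limits are below 50%.

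**3. Size of the shift.** Against exact at 14/20: 50 − 45.7 = 4.3 points at the lower limit and 92 − 88.1 = 3.9 at the upper. Against exact interpolated at 71%: 3.3 and 3.2. The shift is therefore 3 to 4 points at both ends.

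**4. The other cited rates.** Exact intervals: 11/20 (near 54%) gives 32% to 77%; 8/20 (near 41%) gives 19% to 64%.

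**5. Coverage at n=20.** For a true rate p, add up the binomial probabilities of all counts whose interval contains p. At the rates below, the z and t(19) symmetric intervals give the same coverage.

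| True rate | Symmetric | Exact |
|---|---|---|
| 0.50 | 95.9% | 95.9% |
| 0.60 | 92.8% | 96.3% |
| 0.71 | 94.4% | 97.7% |
| 0.75 | 89.5% | 96.2% |
| 0.80 | 92.1% | 97.8% |

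The symmetric form falls short at most of these rates, only slightly at 0.71 itself and most at 0.75.

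**The case against.** The strongest reply is that G1 contains no arithmetic error. It names no method, its figure follows from its own inputs by a recognisable approximation, and the total width of 42 points matches the exact width of 42.4 at 14/20. That stands. A reader might infer that the trial lacks the precision it claims, or that the interval is simply invalid. The documents and the recalculation do not support either reading: the width is right and the placement is off.

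A second reply is that 50% is not a decision boundary. That also stands. A reader might infer that the interval has to exclude 50%, because the power sentence uses the same number. G1 does not link the two figures, and G2 sets no threshold for its interval.

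Third, the 71% comes from a post-viral cohort, the closest population cited, and G1 discloses that it was not COVID-19. The cohorts behind 54% and 41% were mixed, and the latter had not responded to steroids. Choosing 71% is therefore defensible. A reader might also infer that the 71% counts any improvement, however slight, but section B states no threshold, so this can be neither confirmed nor ruled out.

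What the reply does not remove is the 50% floor. At 14/20 it fails under the exact and Wilson methods, and under the t(19) form itself.

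**Conclusion.** The error bars in G1 are wrong as written, and the severity is minor. Both limits are about 3 to 4 points too high against the exact interval; at 14/20 the exact limits are 46% and 88%. Against Wilson the lower limit is about 2 points too high (48.1%) and the upper about 6.5 (85.5%). The 50% lower limit is not supported.

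This rests on n=20 with complete data, a 71% planning rate, and 14/20 as the result that represents it. One more responder would change the picture: at 15/20 the exact lower limit is 50.9%.

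The G2 part is a risk rather than a demonstrated fault, because G2 does not say which interval it will use. The point does not show that 20 participants are too few. G1 also relies on feasibility and on a separate power statement, so the interval should not be read as the main justification for the sample size.

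**What to change.** **G1.** Replace the interval sentence with exact 95% intervals at n=20: 14/20 gives 46% to 88%, 11/20 gives 32% to 77%, and 8/20 gives 19% to 64%. Name the method. Say that the last two correspond to the other response rates in section B and that those cohorts had mixed etiologies. Add that no improvement threshold is given for the 71%, so the rate under this trial's moderate-or-greater rule may differ.

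**G2.** Name one method, exact (Clopper-Pearson) or Wilson, for the primary responder proportion before the data are analysed, and do not use the symmetric form from G1. Exact keeps coverage at or above 95%. Wilson is narrower, and its coverage is nearer 95% on average but can dip slightly below.

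**Cost.** A few sentences of protocol text and a slightly less favourable stated lower limit. The sample size, visits and procedures do not change.

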Chronic olfactory dysfunction from the COVID-19 pandemic is a growing public health crisis with up to 1.2 million people in the United States affected. Olfactory dysfunction impacts one's quality of life significantly by decreasing the enjoyment of foods, creating environmental safety concerns, and affecting one's ability to perform certain jobs. Olfactory dysfunction is also an independent predictor of anxiety, depression, and even mortality. While the pandemic has increased the interest by the scientific community in combating the burgeoning health crisis, few effective treatments currently exist for olfactory dysfunction. Furthermore, patients impacted by "long COVID," or chronic symptoms after an acute COVID-19 infection, experience impairments other than olfactory and gustatory dysfunction, such as chronic dyspnea, impaired memory and concentration, and severe fatigue. These symptoms have been hypothesized to be a result of sympathetic positive feedback loops and dysautonomia. Stellate ganglion blocks have been proposed to treat this hyper-sympathetic activation by blocking the sympathetic neuronal firing and resetting the balance of the autonomic nervous system. Studies prior to the COVID-19 pandemic have supported a beneficial effect of stellate ganglion blocks on olfactory dysfunction, and recent news reports and a published case series have described a dramatic benefit in both olfactory function and other long COVID symptoms in patients receiving stellate ganglion blocks. Therefore, we propose a single cohort prospective study to generate pilot data on the efficacy and safety of sequential stellate ganglion blocks for the treatment of COVID-19-induced olfactory dysfunction and other long COVID symptoms.

A2 Primary Hypothesis

Stellate ganglion block is effective and safe in improving both objective and subjective olfactory dysfunction in patients with chronic COVID-19-induced olfactory impairment.

A3 Purpose of the Study Protocol

The purpose of this study is to evaluate the efficacy of sequential stellate ganglion blocks for the treatment of chronic COVID-19-associated olfactory dysfunction in order to treat the growing population of people with long-term olfactory dysfunction as a result of the pandemic.

B Background and Rationale

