Eligible patients who present to clinic or respond to advertisements will be approached by a research team member to review the informed consent process and thoroughly discuss the research protocol, potential benefits, and risks of the study. The informed consent discussion will take place with the patient and any available family members over the phone or in person, whichever the potential participant prefers. Any subsequent questions or concerns from the potential participant and any family members will also be addressed at that time. After discussion, the patient will be asked to re-summarize the steps involved in the study to ensure understanding. If interested, written consent in

person will be obtained prior to undergoing SGB. Patients will be reminded that study participation is voluntary and will in no way affect their current or future care.

2.d Randomization Method and Blinding

No randomization or blinding will take place.

2.e Risks and Benefits

2.f Early Withdrawal of Subjects

During the informed consent process, participants will be informed that they may withdraw at any point during the study, including before, during, or after their first SGB. Participants will face no penalty or negative consequences for withdrawing from the study.

E3 Study Drug

3.a Description

3.b Treatment Regimen

The ultrasound-guided stellate ganglion blocks (SGBs) will be performed by [name], a board-certified anesthesiologist and pain management specialist who has extensive experience performing SGBs.

Patients will remain NPO for 8 hours prior to the block. If needed, they can take morning medications with a small sip of water. Using ultrasound guidance, the transverse process of C6 will be identified and confirmed. A 27-gauge needle will be used to localize the superficial skin with 1% lidocaine. Color-doppler will be used to identify vessels. Then, a 21-gauge ultrasound needle will be advanced using an in-plane technique from lateral to medial. After negative aspiration, a test dose of 2 ml of 1% lidocaine will be injected. If tolerated, 6-8 ml of 1% mepivacaine local anesthetic will be deposited beneath the prevertebral fascia and above the longus coli muscle. Total local anesthetic will be determined using a maximum total combined dose of 4.5mg/kg lidocaine and 4.5mg/kg mepivacaine.

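### The 80% power in G1 cannot be reproduced from its stated inputs and belongs to no analysis in the plan: Fisher's exact test compares two groups, and this trial has one cohort

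*Combined protocol and SAP*

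**What the plan says.** G1 first says: "Sample size estimate for the proposed study is based both on feasibility and previous data". It then says: "A power analysis was performed using Fisher's exact test in G-Power 3.1.2". Next comes a precision statement: with an expected response of 71% and 20 participants, the 95% interval is 0.71 ± 0.21, or 50% to 92%. The last sentence says that 20 participants in total are needed to "detect with 80% power at the 2-sided alpha level of 0.05 a within-subjects response rate of 50% or more", where response is a clinically meaningful change on the CGI-I. G1 gives no null rate, comparator rate or second group.

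Sections B and D1 call the study a "single cohort prospective study to generate pilot data". Section E2, item 2.d, says: "No randomization or blinding will take place".

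G2 sets out the primary analysis: "The effect of the intervention will be measured as the proportion of participants reporting" that smell is at least moderately better, with a 95% confidence interval. It names no hypothesis test for this outcome and no reference value.

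Section B gives two response figures from earlier studies that bear on the question. In the 2003 study on which G1 relies, subjective smell improved in "27 (71%) of the treated participants compared to zero (0%) of the controls" (38 treated, 13 untreated). In the 2013 series of 37 treated participants, "15 (41%) were determined to be responsive".

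**The concern.** A Fisher's exact power calculation takes two group rates and two group sizes. A one-sample calculation takes a null rate and a true rate. G1 supplies one rate for the power statement, 50%, and does not say whether it is the null or the rate to be detected. The reader cannot tell which test the 80% refers to, and G2 offers no test to attach it to.

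What is at stake is how the sample size and the result are read. A reader is told that 20 participants are required for a powered two-sided test. G2 says the interval will be used to judge whether a clinically meaningful difference is plausible. A reader could take 50% from G1 as that benchmark and believe the trial has 80% power against it. At the expected 71% it has about 46%.

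**Working it through.** **Inputs.** From G1: n = 20 in total, two-sided α = 0.05, stated power 80%, expected rate 0.71, rate in the power sentence 0.50. From section B: 0/13 untreated responders, 27/38 (71%) treated responders, and 15/37 (40.5%, printed as 41%) responders in the later treated series.

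**The precision figure in G1 reproduces.** SE = √(0.71 × 0.29 / 20) = 0.1015. With t(19 df) = 2.093 the half-width is 0.212, giving 0.498 to 0.922, which is G1's 50% to 92%. With 1.96 it is 0.199, giving 0.511 to 0.909. G1's interval is therefore t-based and is not an error.

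**The 80% does not.** I first take 50% as the rate to detect, the natural sense of the sentence.

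*1. One-sample exact binomial test, equal-tailed.* Reject when X ≥ r, where r is the smallest count with P(X ≥ r | p₀) ≤ 0.025. Power = P(X ≥ r | 0.50). The lower rejection tail adds a negligible amount.

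| Null p₀ | r | P(X ≥ r at null) | Power at 50% |
|---|---|---|---|
| 0% | 1 | 0 | 1 − 0.5²⁰ ≈ 1.000 |
| 10% | 6 | 0.0113 | 0.979 |
| 19% | 8 | 0.0241 | 0.868 |
| 20% | 9 | 0.0100 | 0.748 |
| 25% | 10 | 0.0139 | 0.588 |

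Power is at least 0.80 for nulls up to 19.1%. It then drops from 0.868 to 0.748 as the rule moves from 8/20 to 9/20, so under this exact test no null gives 80% itself. Under the minimum-likelihood two-sided convention the step falls just above 20%, so a 20% null gives 0.868. The step sizes do not change.

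*2. Paired sign test, the within-subjects reading.* This needs no reference rate but does need a worsening rate. Full trinomial enumeration with P(improve) = 0.50 and the rest unchanged:

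| P(worsen) | Power |
|---|---|
| 0 | 0.979 |
| 3% | 0.870 |
| 4.6% | 0.802 |
| 5% | 0.785 |
| 10% | 0.573 |

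Power is about 80% only near 4.6% worsening, a figure G1 does not give.

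*3. Fisher's exact test, by enumeration of both binomials, 50% against 0%.*

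| Layout | Sides | Power |
|---|---|---|
| 10 + 10 | two | 0.623 |
| 10 + 10 | one | 0.828 |
| 20 + 20 | two | 0.994 |
| 20 against the 13 earlier untreated controls | two | 0.942 |

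*4. The other role for 50%: null 50%, truth 71%.* P(X ≥ 15 | 0.50) = 0.0207, so r = 15. Power = P(X ≥ 15 | 0.71) = 0.455.

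*5. A near-match from section B's rates: null 15/37, truth 71%.* P(X ≥ 13 | 15/37) = 0.0237, so r = 13 and power = P(X ≥ 13 | 0.71) = 0.802. If the null is entered as the rounded 41%, r becomes 14 and power is 0.646.

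**The case against.** Three points can be put on the plan's side.

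First, values near 80% do exist. The one-sided 10 + 10 Fisher test gives 83%. The 15/37 null with a 71% truth gives 80.2%. A normal approximation with a true rate of 50% gives 81.1% at a 22% null and 77.8% at 23%, so it crosses 80% in between. All of this is correct, but none of it explains G1. G1 says two-sided. It names no null of 41%, 22% or 23%. The 15/37 series is itself a treated group, that reading would detect 71% rather than 50%, it would not use Fisher's test, and it fails at the rounded figure. I cannot exclude some further set of unstated inputs that gives 80%. Having to search for one is the reproducibility problem.

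Second, a two-group Fisher test could have an external control, namely the 13 untreated participants of the 2003 study. That is a coherent layout, but it gives 94%, not 80%, and G2 plans no such comparison.

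Third, the fault may be an omitted input rather than a wrong sum, and with a null low enough the 80% would be an understatement. That is fair: for any null up to 19.1%, including the 0/13 untreated rate, the exact one-sample test has at least 80% power at 50%. Supplying a null would make a power figure checkable. It would not make Fisher's test the right one for a single cohort, and it would not put a test into G2.

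It is also true that this is a pilot whose planned inference is already an estimate with an interval. That limits the consequence. It does not support the sentence as written.

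**Conclusion.** The concern holds. G1's power claim names a two-group test for a one-group trial, omits the null or comparator rate, and matches no analysis in G2. Across the readings above, two-sided power with a total of 20 participants runs from 45.5% (null 50%, truth 71%) to about 100% (null 0%, truth 50%), against a stated 80%. These figures assume that all 20 participants are analysed and that an exact two-sided test is used. The equal-tailed convention is used for the one-sample results.

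The effect is confined to the sample-size justification. No decision rule uses the 80%, the precision statement reproduces, and feasibility is an independent ground for 20. The sample size and the planned estimate can stand. The power claim, as written, cannot. This should be corrected, but it does not call the design into question.

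**What to change.** Delete the Fisher's exact sentence and the 80% power sentence from G1. Justify 20 participants by feasibility and interval precision, and name the interval method. For example, 14/20 responders (70%) would give an exact (Clopper–Pearson) 95% interval of 46% to 88%. G1's present interval is t-based, so G1 and G2 should name the same method. State in both sections that the trial estimates a response rate with a 95% interval and makes no powered test of efficacy.

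If the sponsor prefers to keep a power claim, G1 and G2 should both name a test suited to one cohort. They should state its null rate (or assumed worsening rate) with a justification, and report the exact power that results.

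The cost is rewording in G1 and one sentence in G2, with no added participants, visits or procedures. The downside is that the first option withdraws the 80% figure and the second may replace it with a less favourable one.

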heart palpitations, and orthostatic dizziness, also improved at the one week and two-month follow-up time points. The authors concluded that although the sample size is limited, SGB may have a significant impact on the dysautonomia caused by COVID-19 and improve long COVID symptoms, giving rationale to conduct a larger study. Therefore, we propose a single cohort prospective study to generate pilot data on the effectiveness and safety of sequential stellate ganglion blocks for the treatment of COVID-19-induced olfactory dysfunction and other long COVID symptoms.

D2 Dose Rationale and Risk/Benefits

The stellate ganglion block has been used for decades with the assistance of fluoroscopy and has been modified in the present day by using ultrasound to improve visualization. Substantial data has been generated on the safety and tolerability of the procedure in other conditions, such as post-traumatic stress disorder (PTSD). One study of 250 SGBs for PTSD performed by an experienced pain management provider resulted in zero post-procedural or delayed complications. Of 110 participants in the study who returned completed surveys, 100% of the patients said they would recommend the procedure to a friend, and 95% stated that they would be willing to undergo as many repeat procedures as necessary based on the minimal discomfort and tolerable side effects.²⁸ A temporary Horner's syndrome is an expected outcome of SGB and improves over the course of a few hours.

Risks of lidocaine injection include: drowsiness, dizziness, nausea, vomiting, feeling hot or cold, confusion, ringing in your ears, blurred vision, or double vision. However, these side effects are all rare when used at the maximum total combined dose of 4.5mg/kg lidocaine and 4.5mg/kg mepivacaine. We will strictly following this dosing guideline.

E Study Design

E1 Overview or Design Summary

The study will be a single center, unblinded, prospective cohort study conducted at Washington University School of Medicine.

E2 Subject Selection

2.a Inclusion Criteria

- 1) Adults age 18 to 70
- 2) Diagnosis of COVID at least 12 months prior to study enrollment with self-reported olfactory dysfunction
- 3) Objective olfactory dysfunction due to COVID-19 that has persisted despite viral recovery, as defined by the UPSIT (≤ 34 in women, ≤ 33 in men)

-
- 4) Ability to read, write, and understand English

2.a Exclusion Criteria

- 1) History of smell loss prior to COVID-19 infection

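### Does G2 need a stated reference response rate before its 95% confidence interval can be interpreted?

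*Combined protocol and SAP*

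**What the plan says.** E1 describes a "single center, unblinded, prospective cohort study", and E2 (2.d) states that nobody is randomized. G2 measures the effect as the proportion of participants who rate their smell as at least moderately better than before the block. C3, under the CGI-I scale, sets the same individual threshold, assessed at 1 month. G2 then says: "The 95% confidence interval around this effect size will be determined to assess the precision of the observed effect", and gives the interval a second use, to judge "whether a clinically meaningful difference is plausible given the observed results". It names no responder rate for that purpose.

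G1 contains two relevant figures. One is a planning interval of 0.71 ± 0.21 at 20 participants, described as "resulting in a true response rate likely between 50% and 92" percent. The other, in the next sentence, is "a within-subjects response rate of 50% or more", to be detected with 80% power at a two-sided 0.05 level and tied to clinically meaningful change on the CGI-I. G1 does not say what that 50% is compared with, and G2 does not refer to it.

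**The concern.** A single proportion shows a difference only against some other rate. With one cohort, that rate has to come from outside the data, and G2 supplies none. Its opening sentence, which plans to "describe distribution of baseline characteristics in each of the study groups", even reads as if there were a comparison. G1's 50% to 92% does not fill the gap, because it shows the precision expected if 71% respond.

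The interval is the only inference G2 states for the primary outcome, and the hypothesis in A2 is that "Stellate ganglion block is effective and safe in improving both objective and subjective olfactory dysfunction". In an unblinded study with a self-reported outcome, a benchmark chosen after the data are seen could turn one result into a claim of success, an inconclusive finding, or agreement with earlier work.

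**Working it through.** **Inputs.** n = 20, expected rate 71%, half-width 0.21 and the 50% detection rate are from G1. Response rates of 71% (27 of 38), 54% (7 of 13) and 41% (15 of 37) are from the three earlier series of this block in section B, used only as illustrative true rates. Treating 50% as the benchmark is an assumption.

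**Step 1: the plan's own interval.** The standard error is √(0.71 × 0.29 / 20) = 0.1015. With the t quantile on 19 degrees of freedom, 2.093 × 0.1015 = 0.212, so the interval is 0.498 to 0.922. This matches G1. With 1.96 the half-width is 0.199 (51.1% to 90.9%). The planning figure is sound as a statement of expected precision.

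**Step 2: the interval against 50%.** For x responders, the exact (Clopper-Pearson) lower limit is the 0.025 quantile of Beta(x, 21 − x), and the upper limit is the 0.975 quantile of Beta(x + 1, 20 − x). The t-symmetric interval is x/20 ± 2.093 × √((x/20)(1 − x/20)/20).

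| Responders | Limit | Exact | Wilson | t-symmetric |
|---|---|---|---|---|
| 5/20 | upper | 49.1% | 46.9% | 45.3% |
| 6/20 | upper | 54.3% | 51.9% | 51.4% |
| 14/20 | lower | 45.7% | 48.1% | 48.6% |
| 15/20 | lower | 50.9% | 53.1% | 54.7% |

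Under all three methods the interval contains 50% for 6 to 14 responders and lies above it from 15. At this benchmark, leaving the interval method unnamed does not matter.

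**Step 3: how often a result falls in 6 to 14.** Summing binomial probabilities with n = 20 gives 89.0% at a true rate of 41%, 94.6% at 54% and 54.5% at 71%. The chance of 15 or more at 71% is 45.5%. If the reading were truly open, it would often matter.

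**Step 4: can 50% be the null rate behind G1's 80% power?** With 20 participants, the exact two-sided test of 50% has 45.5% power at a true 71%. It reaches 80.4% only at a true 80%. For stable 80% power at 71%, about 49 participants would be needed. If 50% is instead the alternative, power depends on the unstated null: 86.8% against 19%, 74.8% against 20%. The role of 50% therefore cannot be recovered from the figures given.

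**Step 5: the case that looks worst.** Ten of 20 responders gives an exact interval of 27.2% to 72.8%. That is above 25%, contains 50% and reaches 71%. Two features weaken the example.

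- The Wilson interval is 29.9% to 70.1%, which does not reach 71%.
- The 25% is not in the plan. It rounds the exact upper limit for no improvement in the earlier study where "13 participants remained untreated as controls": 1 − 0.025^(1/13) = 24.7%. The rounding matters: the interval for 1 of 20 has an upper limit of 24.9%, which reaches 24.7% but not 25%.

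All three descriptions can also be true of one interval at once. They are not competing verdicts.

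**The case for a change.** The strongest case for a change is that pilot status does not excuse an interpretive clause with no benchmark. A2 speaks of effectiveness, the outcome is subjective and uncontrolled, and one or two sentences would settle how the interval is read before the data arrive. If the sponsor could not justify a benchmark, the clause could be deleted at no cost.

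Part of this stands. G2 does not say which responder rate is clinically meaningful, and G1 leaves the role of its 50% undefined. The reference to study groups is a slip in a one-cohort study, and G1's wording about where the true rate likely lies is loose for a planning interval.

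The rest is weaker. The clause can be carried out: G2 compares each participant's smell with the state before the block, G1 speaks of response within subjects, and C3 fixes the individual threshold. The interval then gives the range of plausible rates of meaningful change in individuals. For an interval, plausible ordinarily means contained in it. The split between 6 and 14 responders arises by setting that reading against a stricter one, wholly above the benchmark, which the text does not suggest. A rule that sorts results into supported, inconclusive and not supported is a preference for a study whose stated aim is pilot data, and its key number would have to come from the sponsor, because the documents justify none.

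**Conclusion.** No change to the plan is called for. There is a real but minor gap in detail: G2 is not linked to the 50% in G1. If 50% is taken as the benchmark and plausible has its usual meaning, the clause asks only whether the interval reaches 50%, which it does from 6 of 20 responders under all three interval methods. If a reader prefers the stricter standard of 15 of 20, the published proportion and interval let that reader apply it.

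The primary estimate, its interval and the sample size of 20 are the same under either reading. The conclusion rests on the study being reported as what it is, an uncontrolled pilot estimate. The 45.5% chance of clearing 50% at a true 71% shows that 20 participants would not support a confirmatory claim against that rate, and G2 does not plan one. The comparison rate missing from G1's power sentence is a separate matter and does not affect how the interval is computed or reported.
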